9.1. Statistical Hypotheses

Bioequivalence of the OD tablet without water versus the current IR tablet will be established if the 90% confidence interval (CI) of the ratio of geometric least square means for area under the concentration versus time curve (AUC) from time zero to infinity ($AUC[(0-\infty)]$), AUC from time zero to time t , where t is the last time point with a measurable concentration ($AUC[0-t_{last}]$), and maximum observed drug concentration (C_{max}) is within the testing boundaries of 0.8 and 1.25.

9.2. Sample Size Determination

A total of 36 participants are required complete the study to establish equivalence between the OD tablet formulation without water and the current IR tablet, based on the PK parameters measured.

Given the 6×3 design this would mean at least 6 participants would be randomly assigned to each of the 6 dosing sequences. The calculated total number of participants assumes 90% power for the two one-sided test (TOST) for equivalence with a significance level of 5%, analogous to a 90% CI. Further, this is based on:

- a nominally assigned true mean ratio of 1.05
- a coefficient of variation for C_{max} of 24.1%
- ratio testing boundaries of 0.8 and 1.25.

Assuming that 25% of participants will drop out or fail to provide full study data, approximately 48 participants should be enrolled to ensure that 36 participants, 6 per treatment sequence, will complete the study.

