4.1. Overall Design

Study H8H-MC-LAIA (LAIA) is a Phase 1, open-label, randomized, single-dose, 3-way crossover study in healthy participants. Approximately 48 participants will be enrolled such that 36 participants, 6 per treatment sequence, complete the study.

Screening

All participants will be screened within 28 days prior to enrollment.

Treatment and Assessment Period

Eligible participants will take part in 3 separate dosing periods. In each period, participants will be admitted to the CRU on Day -1 and remain resident in the CRU until discharge on Day 6. At the discretion of the investigator, participants may remain resident in the CRU for the entirety of the study, i.e., from admission to the CRU on Day -1 of Period 1 until discharge from the CRU on Day 6 of Period 3, after all assessments have been completed.

There will be a washout period of ≥ 5 days between the day of dosing in 1 period and the day of dosing in the subsequent period. Days 5 and 6 of Period 1 and 2 may coincide with Days -1 and 1 of Period 2 and 3, respectively, provided the required washout between lasmiditan doses is observed.

On Day 1 of Period 1, participants will be equally randomized to receive a 100-mg oral dose in 1 of 6 dosing sequences in each of 3 dosing periods as shown in [Table LAIA.1](#).

Table LAIA.1. Dosing Sequences for Protocol H8H-MC-LAIA

Sequence	Period 1	Period 2	Period 3
1	IR (reference)	OD without water (test)	OD with water (test)
2	IR (reference)	OD with water (test)	OD without water (test)
3	OD without water (test)	OD with water (test)	IR (reference)
4	OD without water (test)	IR (reference)	OD with water (test)
5	OD with water (test)	IR (reference)	OD without water (test)
6	OD with water (test)	OD without water (test)	IR (reference)

Abbreviations: IR = immediate release; OD = oral disintegrating.

Pharmacokinetic blood sampling and safety assessments, including vital sign measurements, physical examinations, clinical laboratory tests, electrocardiograms (ECGs), and AE recording will be performed according to the SoA (Section [1.3](#)).

Follow-up

Day 6 of Period 3 will be considered the final visit of the study.

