7.2. Participant Discontinuation/Withdrawal from the Study

A participant may withdraw from the study:

- at any time at his/her own request
- at the request of his/her designee (for example, parents or legal guardian)
- at the discretion of the investigator for safety, behavioral, compliance, or administrative reasons
- if the participant becomes pregnant during the study
- if enrollment in any other clinical study involving an investigational product or enrollment in any other type of medical research judged not to be scientifically or medically compatible with this study.

Discontinuation is expected to be uncommon.

At the time of discontinuing from the study, if possible, an early discontinuation visit should be conducted, as shown in the SoA (Section 1.3). See SoA for data to be collected at the time of study discontinuation and follow-up and for any further evaluations that need to be completed. The participant will be permanently discontinued both from the study intervention and from the study at that time.

If the participant withdraws consent for disclosure of future information, the sponsor may retain and continue to use any data collected before such a withdrawal of consent. If a participant withdraws from the study, he/she may request destruction of any samples taken and not tested, and the investigator must document this in the site study records.

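### Does enrolling 48 really guarantee 36 completers with 6 in every sequence, and does it matter that it does not?

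*Protocol*

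**What the plan says.** Protocol 9.2 sets the target for comparing the OD tablet without water with the IR tablet: "A total of 36 participants are required complete the study to establish equivalence". The calculation "assumes 90% power for the two one-sided test (TOST) for equivalence with a significance level of 5%, analogous to a 90% CI", with "a nominally assigned true mean ratio of 1.05", a Cmax coefficient of variation of 24.1% and limits of 0.8 and 1.25. For the six sequences the section asks that "at least 6 participants would be randomly assigned to each of the 6 dosing sequences".

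Enrolment is then raised for losses. The allowance is worded "Assuming that 25% of participants will drop out or fail to provide full study data", and the conclusion drawn from it is that "approximately 48 participants should be enrolled to ensure that 36 participants, 6 per treatment sequence, will complete the study". SAP 7 repeats this, and the protocol synopsis also speaks of ensuring 36. Protocol 4.1 and SAP 5 give the same numbers as an aim without that verb. Protocol 4.1 states that "participants will be equally randomized to receive a 100-mg oral dose in 1 of 6 dosing sequences", which implies 8 per sequence if exactly 48 enter; the figure 8 is derived, not stated.

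Protocol 7.2 says of withdrawal from the study: "Discontinuation is expected to be uncommon". The documents contain no rule for replacing participants. Protocol 9.4.2.2 and SAP 9.3.2 keep all valid PK data in the model, including data from participants who miss a period.

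**The concern.** Three things look wrong together. First, dividing 36 by 0.75 yields the enrolment at which 36 complete on average. The wording turns that average into an assurance, and no replacement rule makes up a shortfall. Second, the assurance extends to 6 completers in each sequence, a much harder condition than 36 in total. Third, a 25% loss allowance sits oddly beside a statement that discontinuation will be uncommon.

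If 36 completers and the 6-per-sequence balance were truly required, the trial would be likely to miss its own target, and a reader might take 35 completers, or 5 in one sequence, as a failed design. If the power claim depended on that target, the study could also be underpowered.

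**Working it through.** **Inputs.** From Protocol 9.2: 36 completers, 48 enrolled, 25% loss, true ratio 1.05, Cmax CV 24.1%, limits 0.80 to 1.25, TOST at 5%, 90% power. From Protocol 4.1: equal allocation to six sequences, so 48/6 = 8 each. Assumptions not in the documents: losses are independent, exactly 8 are randomized per sequence, and 24.1% is the within-participant CV.

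**Reproducing the plan's figures.**

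- Enrolment: 36/(1 − 0.25) = 48.
- Completers: σ = √ln(1 + 0.241²) = 0.2376 on the log scale, and the standard error of a treatment difference is σ√(2/n). At n = 36 this is 0.2376 × √(2/36) = 0.0560.

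Exact TOST power:

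| Completers n | df = 2n − 4 (three-period model) | df = n − 2 (two-treatment crossover) |
|---|---|---|
| 30 | 87.4% | 86.7% |
| 32 | 89.4% | 88.7% |
| 33 | 90.2% | 89.6% |
| 34 | 91.0% | 90.4% |
| 36 | 92.4% | 91.9% |
| 48 | 97.3% | 97.1% |

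Power first reaches 90% at 33 or 34 completers, depending on the degrees of freedom. Rounding up to a multiple of 6 gives 36, so both of the plan's numbers reproduce.

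**What 48 enrolled delivers at 25% loss.**

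- Expected completers: 48 × 0.75 = 36.
- P(at least 36 of 48), Binomial(48, 0.75): 0.577.
- P(at least 6 of 8 in one sequence), Binomial(8, 0.75): 0.311 + 0.267 + 0.100 = 0.679 after rounding.
- P(at least 6 in all six sequences): 0.6785⁶ = 0.098.
- If exactly 12 are lost, 6 per sequence requires exactly two losses in each: C(8,2)⁶/C(48,12) = 0.0069, or 0.7%.

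**Sensitivity to the loss rate.** The 5% and 10% rows are assumed readings of uncommon; the documents give no figure.

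| Loss | P(at least 36 in total) | P(at least 6 in every sequence) |
|---|---|---|
| 5% | >99.9% | 96.6% |
| 10% | 99.9% | 79.2% |
| 15% | 97.8% | 51.3% |
| 20% | 85.2% | 25.6% |
| 25% | 57.7% | 9.8% |

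**Effect on power.** Weighting the df = 2n − 4 power by the Binomial(48, 0.75) distribution of completers gives an average of 92.1%. Fewer than 33 complete with probability 0.123, but the shortfall is shallow: power is still 89.4% at 32 and 87.4% at 30, and fewer than 30 complete with probability 0.018. These figures count full completers only, so they ignore the partial data that the model keeps.

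**Does anything depend on 6 per sequence?** The PK population (Protocol 9.3, SAP 8) needs one dose and evaluable PK data. The mixed model has sequence as a fixed effect but needs no balance across sequences. The bioequivalence rule refers only to the 90% confidence intervals. No decision is tied to the completer count.

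**Protocol 7.2 against the 25%.** Section 7.2 concerns withdrawal from the study. The 25% covers dropout together with failure to provide full data. SAP 8, for example, permits exclusion from the PK analysis after early vomiting, which need not involve withdrawal. The two statements have different scopes.

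**The case for a change.** The strongest argument for acting is that the sentence is untrue at the plan's own loss rate and appears in both documents. The total is missed in about 42% of trials (1 − 0.577) and the sequence balance in about 90% (1 − 0.098). The balance fails almost always even if 25% is treated as a fixed count of 12. The plan calls 36 required without saying that this exceeds what 90% power needs, and it does not say how the 25% divides between withdrawals and unusable data. A rewording would cost nothing.

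All of that stands as a remark on wording. It does not reach the design. The sentence is itself conditional and approximate, and the headline 10% tests a condition that nothing in the analysis uses. The two limbs also weaken each other: the 10% needs the full 25% loss, whereas if losses really are uncommon the promise is nearly kept, at least for the total.

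Nor should a replacement sentence name 33 completers as the minimum. That figure becomes 34 under the other degrees of freedom, rests on reading 24.1% as within-participant, and concerns Cmax alone, although bioequivalence requires all three parameters.

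**Conclusion.** No change is needed. The plan's verb overstates an expected value: at 25% loss, 36 or more complete in about 58% of trials and 6 in every sequence in about 10%, given independent losses and 8 randomized per sequence. But the sample size arithmetic is right, and average power for Cmax is about 92% against the stated 90%, taking 24.1% as the within-participant CV. No population, model or success criterion depends on 36 completers or on sequence balance. The 25% allowance and the expectation of few withdrawals are compatible because the allowance is wider. If the text is reopened for another reason, the sponsor could call 36 the expected number and 6 per sequence a target, and note that the 25% includes unusable PK data. That edit is optional and would change no enrolment figure, analysis or result.

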9.3. Populations for Analyses

The following populations are defined:

Population	Description
Enrolled	All participants randomly assigned to study intervention.
Safety	All enrolled participants who received at least 1 dose of study intervention. Participants will be analyzed according to the intervention they actually received.
Pharmacokinetic Analysis	All enrolled participants who received at least 1 dose of study intervention and have evaluable PK data.

9.3.1. Study Participant Disposition

A detailed description of participant disposition will be provided at the end of the study.

9.3.2. Study Participant Characteristics

The participants' age, sex, weight, height, body mass index, race, and other demographic characteristics will be recorded and summarized using descriptive statistics.

9.4. Statistical Analyses

Statistical analysis of this study will be the responsibility of the sponsor or its designee.

Any change to the data analysis methods described in the protocol will require an amendment only if it changes a principal feature of the protocol. Any other change to the data analysis methods described in the protocol, and the justification for making the change, will be described in the statistical analysis plan (SAP) and the clinical study report. Additional exploratory analyses of the data will be conducted as deemed appropriate.

The SAP will be finalized prior to the first participant visit and it will include a more technical and detailed description of the statistical analyses described in this section. This section is a summary of the planned statistical analyses of the most important endpoints including primary and key secondary endpoints.

9.4.1. General Considerations

Data listings will be provided for all data that are databased. Data listings will be provided for all participants up to the point of withdrawal, with any participants excluded from the relevant population highlighted.

Summary statistics and statistical analysis will only be presented for data where detailed in the SAP. Summary statistics and statistical analyses will generally only be performed for participants included in the relevant analysis population. For the calculation of summary statistics and statistical analysis, unrounded data will be used.

9.4.2. Pharmacokinetic Analyses

9.4.2.1. Pharmacokinetic Parameter Estimation

Pharmacokinetic parameter estimates for lasmiditan and M8, based on plasma concentrations, will be calculated by standard noncompartmental methods of analysis and summarized using descriptive statistics.

The primary PK parameters for analysis will be C_{max} , $AUC(0-\infty)$, and AUC from time zero to time t , where t is the last time point with a measurable concentration ($AUC[0-t_{last}]$) of lasmiditan.

Other noncompartmental parameters, such as half-life, apparent clearance, and apparent volume of distribution may be reported.

9.4.2.2. Pharmacokinetic Statistical Inference

Log-transformed $AUC(0-\infty)$, $AUC(0-t_{last})$, and C_{max} of lasmiditan will be evaluated in a linear mixed-effects model with fixed effects for period, sequence, and treatment and a random effect for participant within sequence.

All valid PK data will be included, whether or not the participants completed all 3 periods.

Estimates of geometric least square mean ratios together with the corresponding 90% CIs will be derived for the comparisons of $AUC(0-\infty)$, $AUC(0-t_{last})$, and C_{max} as follows:

- Primary endpoint: lasmiditan OD tablet without water (test) versus lasmiditan IR tablet

- Secondary endpoint: lasmiditan OD tablet with water (test) versus lasmiditan IR tablet.

The 2 lasmiditan formulations will be considered bioequivalent if the 90% CIs of the ratio of geometric least square means falls completely within 0.80 to 1.25.

Values of t_{max} will be analyzed non-parametrically using the Wilcoxon signed rank test. Estimates of the median difference between test and reference formulations based on the observed medians, 90% CIs, and the p-value from the Wilcoxon test will be calculated.

Additional PK analyses may be conducted if deemed appropriate.

9.4.3. Safety Analyses

9.4.3.1. Clinical Evaluation of Safety

All study intervention and protocol procedure AEs will be listed, and, if the frequency of events allows, safety data will be summarized using descriptive methodology.

The incidence of symptoms for each treatment will be presented by severity and by association with study intervention as perceived by the investigator. Symptoms reported to occur prior to enrollment will be distinguished from those reported as new or increased in severity during the study. Each symptom will be classified by the most suitable term from the medical regulatory dictionary.

The number of study intervention-related SAEs will be reported.

9.4.3.2. Statistical Evaluation of Safety

Safety parameters that will be assessed include safety laboratory parameters and vital signs. The parameters will be listed and summarized using standard descriptive statistics. Additional analysis will be performed if warranted upon review of the data.

9.4.4. Product Acceptability and Palatability Analyses

Responses from the product acceptability and palatability questionnaire will be summarized categorically (frequency and percentage).

9.5. Interim Analyses

No interim analyses are planned for this study. If an unplanned interim analysis is deemed necessary for reasons other than a safety concern, the protocol must be amended.

9.6. Data Monitoring Committee (DMC)

Not applicable to this study.

10. Supporting Documentation and Operational Considerations

10.1. Appendix 1: Regulatory, Ethical, and Study Oversight Considerations

10.1.1. Regulatory and Ethical Considerations

This study will be conducted in accordance with the protocol and with the following:

- Consensus ethical principles derived from international guidelines including the Declaration of Helsinki and Council for International Organizations of Medical Sciences (CIOMS) International Ethical Guidelines
- Applicable International Council for Harmonisation (ICH) Good Clinical Practice (GCP) Guidelines
- Applicable laws and regulations.

The protocol, protocol amendments, ICF, IB, and other relevant documents (e.g., advertisements) must be submitted to an IRB/IEC by the investigator and reviewed and approved by the IRB/IEC before the study is initiated.

Any amendments to the protocol will require IRB/IEC approval before implementation of changes made to the study design, except for changes necessary to eliminate an immediate hazard to study participants.

The investigator will be responsible for the following:

- Providing written summaries of the status of the study to the IRB/IEC annually or more frequently in accordance with the requirements, policies, and procedures established by the IRB/IEC
- Notifying the IRB of SAEs or other significant safety findings as required by IRB/IEC procedures
- Providing oversight of the conduct of the study at the site and adherence to requirements of 21 Code of Federal Regulations (CFR), ICH guidelines, the IRB/IEC, European regulation 536/2014 for clinical studies (if applicable), and all other applicable local regulations.

Investigator sites are compensated for participation in the study as detailed in the clinical trial agreement.

10.1.2. Informed Consent Process

The investigator or his/her representative will explain the nature of the study, including the risks and benefits, to the participant or his/her legally authorized representative and answer all questions regarding the study.

Participants must be informed that their participation is voluntary. Participants or their legally authorized representative will be required to sign a statement of informed consent that meets the requirements of 21 CFR 50, local regulations, ICH guidelines, Health Insurance Portability and Accountability Act (HIPAA) requirements, where applicable, and the IRB/IEC or study center.

The medical record must include a statement that written informed consent was obtained before the participant was entered in the study and the date the written consent was obtained. The authorized person obtaining the informed consent must also sign the ICF.

Participants must be re-consented to the most current version of the ICF during their participation in the study.

A copy of the ICF(s) must be provided to the participant or the participant's legally authorized representative and is kept on file.

10.1.3. Data Protection

Participants will be assigned a unique identifier by the sponsor. Any participant records, datasets or tissue samples that are transferred to the sponsor will contain the identifier only; participant names or any information which would make the participant identifiable will not be transferred.

The participant must be informed that his/her personal study-related data will be used by the sponsor in accordance with local data protection law. The level of disclosure must also be explained to the participant who will be required to give consent for their data to be used as described in the informed consent.

The participant must be informed that his/her medical records may be examined by Clinical Quality Assurance auditors or other authorized personnel appointed by the sponsor, by appropriate IRB/IEC members, and by inspectors from regulatory authorities.

The sponsor has processes in place to ensure data protection, information security and data integrity. These processes include appropriate contingency plan(s) for appropriate and timely response in the event of a data security breach.

10.1.4. Dissemination of Clinical Study Data

Communication of Suspended or Terminated Dosing

If a decision is taken to suspend or terminate dosing in the trial due to safety findings, this decision will be communicated by Lilly to all investigators (for example, by phone and/or email) as soon as possible. It will be a requirement that investigators respond upon receipt to confirm that they understand the communication and have taken the appropriate action prior to further dosing any participants with study intervention. Any investigator not responding will be followed up by Lilly personnel prior to any further planned dosing. If a dose is planned imminently, Lilly personnel will immediately, and continually, use all efforts to reach investigators until contact is made and instructions verified.

Reports

The sponsor will disclose a summary of study information, including tabular study results, on publicly available websites where required by local law or regulation.

Data

The sponsor does not proactively share data from Phase 1 clinical trials. Requests for access to Phase 1 clinical trial data are evaluated on a case-by-case basis taking into consideration the ability to anonymize the data and the nature of the data collected.

10.1.5. Data Quality Assurance

All participant data relating to the study will be recorded on printed or electronic CRF unless transmitted to the sponsor or designee electronically (e.g., laboratory data). The investigator is responsible for verifying that data entries are accurate and correct by physically or electronically signing the CRF.

The investigator must maintain accurate documentation (source data) that supports the information entered in the CRF.

The investigator must permit study-related monitoring, audits, IRB/IEC review, and regulatory agency inspections and provide direct access to source data documents.

Monitoring details describing strategy (e.g., risk-based initiatives in operations and quality such as Risk Management and Mitigation Strategies and Analytical Risk-Based Monitoring), methods, responsibilities and requirements, including handling of noncompliance issues and monitoring techniques are provided in the Monitoring Plan.

The sponsor or designee is responsible for the data management of this study including quality checking of the data.

The sponsor assumes accountability for actions delegated to other individuals (e.g., Contract Research Organizations).

Study monitors will perform ongoing source data verification to confirm that data entered into the CRF by authorized site personnel are accurate, complete, and verifiable from source documents; that the safety and rights of participants are being protected; and that the study is being conducted in accordance with the currently approved protocol and any other study agreements, ICH GCP, and all applicable regulatory requirements.

Records and documents, including signed ICFs, pertaining to the conduct of this study must be retained by the investigator for the time period outlined in the Clinical Trial Agreement (CTA) unless local regulations or institutional policies require a longer retention period. No records may be destroyed during the retention period without the written approval of the sponsor. No records may be transferred to another location or party without written notification to the sponsor.

In addition, the sponsor or its representatives will periodically check a sample of the participant data recorded against source documents at the study site. The study may be audited by sponsor or its representatives, and/or regulatory agencies at any time. Investigators will be given notice before an audit occurs.

Data Capture System

The investigator is responsible for ensuring the accuracy, completeness, legibility, and timeliness of the data reported to the sponsor.

An electronic data capture (EDC) system will be used in this study for the collection of CRF data. The investigator maintains a separate source for the data entered by the investigator or designee into the sponsor-provided EDC system. The investigator is responsible for the identification of any data to be considered source and for the confirmation that data reported are accurate and complete by signing the CRF.

Data collected via the sponsor-provided data capture system will be stored at a third party. The investigator will have continuous access to the data during the study and until decommissioning of the data capture system. Prior to decommissioning, the investigator will receive an archival copy of pertinent data for retention.

Data managed by a central vendor, such as laboratory test data, will be stored electronically in the central vendor's database system and reports will be provided to the investigator for review and retention. Data will subsequently be transferred from the central vendor to the sponsor data warehouse.

Data from complaint forms submitted to sponsor will be encoded and stored in the global product complaint management system.

